1.7. BLINDING

There was no blinding after the sealed envelopes had been opened. After randomization, the participants and trial staff were aware of the trial group to which the patient had been allocated.

A completely blinded trial would have required fully dedicated staff. Such a trial would have put pressure on already busy anaesthetists. However, there was an agreement from the departments that the TXA would be given according to the study protocol.

1.8. INTERVENTION

The participants in the intervention arm received TXA (10mg/kg) administered slowly over 5 minutes intravenously (iv) 10 minutes prior to skin incision and prophylactic oxytocin (5 IU iv) slow administration by the anaesthetists on delivery of the baby. Participants in the control group received prophylactic oxytocin (5 IU iv) only on delivery of the baby. 5IU of Oxytocin were administered slowly intravenously as recommended by the WHO in 2012 ⁽¹²⁾. Updated recommendations were then published by WHO in 2018

after ethical approvals had been obtained and came to the attention of the principal investigator after the initial planned period of data collection (1 January 2018 to 31 December 2018) recommending the use of 10IU of oxytocin in the third stage. No change was made to the protocol during the data collection period⁽³⁾. All patients continued to receive 5IU of prophylactic oxytocin.

TXA (10mg/kg) solution for injection from the vial was diluted with 100 – 200ml electrolyte solution such as Normal Saline, Ringers Lactate solution, dextrose/water for injection on the same day it was to be used by the anaesthetist at the dose prescribed. Intravenous administration at a rate of 100mg or fraction thereof over at least 1 minute – usually at least 5 minutes for each patient was done. The administration was to be done at least 10 minutes before skin incision^(32, 33, 37, 38).

No additional prophylactic uterotronics were to be administered to the patient based on the anaesthetist's or surgeon's subjective preferences. Several local surgeons routinely add misoprostol for select cases at caesarean section. A recent local unpublished study conducted in 2017 concluded that adding misoprostol to the routine prophylactic oxytocin did not reduce the occurrence of PPH in patients undergoing low risk elective caesarean section⁽⁵¹⁾. Therefore, additional uterotronics were to be administered only if clinically indicated.

1.9. PHARMACY PLAN

Intravenous oxytocin is dispensed weekly from the pharmacy to theatre, where it is stored in a refrigerator in the custody of the sister-in-charge. All patients undergoing caesarean delivery routinely receive 5IU oxytocin intravenously, administered slowly by the anaesthetist after delivery of the baby at HMH and MNMH. The cold chain is maintained up to the administration of the drug to the patient.

TXA obtained for the study was purchased from Sky Pharmaceuticals (Tranexamic acid 0.1g/ml injection from Pfizer Laboratories, registration number: 75/10.4/574) was kept in theatre. This was done to ensure

an uninterrupted supply of the drug for the trial. The TXA vials were kept in a lockable drug cupboard accessible to the sister-in-charge only, who would only dispense them to the anaesthetist on presentation of a study prescription form. A dispensing register for the TXA was kept in the same cupboard. Patient details and study number, amount of TXA dispensed and wasted were entered into the study register for accountability and to guard against abuse. Please refer to the detailed Pharmacy Plan in **Error! Reference source not found..**

1.10. ASSESSMENT

Data were collected and recorded on the data collection tool. Any adverse event was to be reported on the MCAZ/MRCZ adverse event reporting form.

Vital signs (heart rate, blood pressure, respiratory rate) were recorded before surgery, immediately after placental delivery, and 1 to 2 hours after birth.

Full blood count (FBC), urea & electrolytes (U&E) and liver function tests (LFTs) were performed a day before delivery and on the second day after delivery.

Estimated blood loss (EBL) was determined using the difference in haematocrit values taken before and 48 hours after caesarean delivery according to the formula:

$$= \text{EBV} \times (\text{Preoperative haematocrit} - \text{Postoperative haematocrit})$$

Preoperative haematocrit

Where EBV (estimated blood volume) in ml is equal to the woman's weight in kg \times 85 ⁽³⁸⁾.

As haematocrit values were not consistently available, EBL was also determined using the haemoglobin (Hb) value using the Meunier's formula $BV \times [(Hb_i - Hb_e)/(Hb_e)]$, where BV is blood volume, Hb_i is initial Hb, and Hb_e is end Hb⁽⁵²⁾.

Standard EBL based on visual estimates made by anaesthetist after assessment of patient's linen and abdominal swabs was also recorded.

The calculated method and visual estimation of blood loss were used in this study. Although visual estimation is the method used frequently by anaesthetists to estimate blood loss, it has been demonstrated as inaccurate in repeated studies. Its continued use in clinical practice is related to tradition and ease of use. This method was compared with the calculated method by Stafford et. al. who noted that these calculations could be inaccurate based on the hydration status of women, particularly related to intravenous loading conducted during regional anaesthesia (>90% had an epidural), or with pregnancy-induced hypertension. They also acknowledged that maternal physiologic changes may alter the haematocrit changes. Plasma volume increases by on average 1.25 litres in all pregnant women, and all will undergo fluid changes post-delivery^(23, 53, 54). In addition, all of the participants received intravenous fluids as they are surgical patients. Therefore, any effects on the haematocrit of the physiological changes or IV fluids happened in all the participants as the plasma volume changes were universal to all pregnant women. Secondly, we intended to do a subgroup analysis of women who had pregnancy-induced-hypertension. Women with Eclampsia/HELLP syndrome were excluded from the study. As visual estimation is the method traditionally used at both hospitals, we used this together with the more objective calculated method for comparison to determine blood loss.

Refer to **Error! Reference source not found.** for the patient flow in the study.

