1.1. RESEARCH DESIGN

Open-label parallel randomized control trial in which women included in the trial were assigned either TXA or no TXA. No changes were made to the trial design after commencement.

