1.11. STATISTICAL METHODS

Data analysis was conducted using Stata v15 (Stata Statistical Software: Release 15. College Station, TX: StataCorp LLC) following the CONSORT guidelines for reporting RCTs⁽⁵⁵⁾.

The primary analysis compared women given a low dose of TXA (10mg/kg) administered 10 minutes before elective caesarean section with prophylactic oxytocin administration to those given prophylactic oxytocin alone.

Baseline characteristics were compared between the groups to check the adequacy of randomization. Differences between patients lost to follow-up and included patients were also assessed. The intention-to-treat analysis was followed. This is a statistical concept whereby every participant in the study is accounted for in the analysis according to the randomization treatment assignment regardless of whether there is noncompliance, protocol deviations, withdrawal from the study, and anything happens after randomization⁽⁵⁶⁾.

Categorical data were reported using frequencies and proportions while continuous data were summarized using means and standard deviations for normally distributed data, and medians and quartile range where data was not normally distributed. Comparisons for categorical data were done using the chi-square test or Fisher's exact test when the sample size was small.

For continuous data, the t-test was used to compare differences between the groups and the analysis of variance (ANOVA) was used for comparing more than two groups. Where data were not normally distributed, the nonparametric Kruskal Wallis test was used to compare differences in continuous outcome for more than two groups. The Mann-Whitney U test was used to compare two groups where data were not normally distributed. Effect estimates were presented with relative risk measures and associated 95% confidence intervals. Any subgroup analysis was conducted as the primary analysis.

An analysis was conducted after 506 participants had been recruited to check if there are any significant differences in adverse events in the two groups.

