1.14. OUTCOMES

1.14.1. Primary Outcome

1. Incidence of PPH defined by blood loss equal to or exceeding 1,000 ml following elective caesarean section

- Based on calculated estimates.

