1.14.2. Secondary Outcomes

1. Incidence of PPH defined by blood loss equal to or exceeding 1000 ml following elective caesarean section

- Based on visual estimation

2. Estimated blood loss during caesarean section

- Based on visual estimate of blood loss and calculated estimates

3. Need for blood transfusion

- Mean or median number of units of red blood cells transfused up to day 2 postpartum

4. Use of additional uterotonicics (such as oxytocin infusion or prostaglandins)

- Number of participants who required additional uterotronics

5. Incidence of emergency surgical interventions for PPH up to day 2 post-surgery

6. Mean change in HCT up to day 2 post-surgery

- Difference between the HCT on the day before surgery and day 2 post-surgery

7. Mean peripartum change in haemoglobin up to day 2 post-surgery

- Difference between the haemoglobin on the day before surgery and at day 2 post-delivery

8. Duration of mother's hospital stay

9. TXA side effects

- number of participants with headache, anaphylaxis, nausea, diarrhoea, dizziness, fatigue, nasal sinus complaints, transient visual disturbances, abdominal pain, complaints of feeling faint, reported by anaesthetists and theatre staff [time frame: up to discharge from the recovery ward on day of surgery]
- number of participants with deep venous thrombosis, pulmonary embolism, myocardial infarction, or any thrombotic event confirmed by laboratory investigations up to day 2 post-surgery
- number of participants with seizures up to day 2 post-surgery
- number of participants with renal failure (defined by the need for dialysis) up to day 2 post-surgery
- number of participants with hypotension reported by anaesthetists and theatre staff [time frame: up to discharge from the recovery ward on day of surgery]
- Vital signs before surgery
 - Heart rate before surgery
 - Systolic BP before surgery
 - Diastolic BP before surgery

- Vital signs after placental delivery
 - Heart rate after delivery of the placenta
 - Systolic BP after delivery of the placenta
 - Diastolic BP after delivery of the placenta
- Post-caesarean delivery creatinine (mg/dL)
- Postoperative urea g/L
- Postoperative aspartate transaminase (IU/L)
- Postoperative alanine transaminase (IU/L)
- Postoperative total bilirubin (IU/L)

10. Neonatal outcomes

- Birth weight in grams determined on the date of delivery
- Apgar scores at 1 and 5 minutes on the date of delivery

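### Calculated blood loss for the primary endpoint ignores red cells transfused before the day-2 sample, so a transfused woman with true PPH can be counted as having none, and no sensitivity analysis checks this

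*Combined protocol and SAP*

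**What the plan says.** Section 1.14.1 (Primary Outcome) sets the endpoint as "Incidence of PPH defined by blood loss equal to or exceeding 1,000 ml following elective caesarean section", taken from calculated rather than visual estimates.

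Section 1.10 (Assessment) gives two calculations:

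- Haematocrit: "Estimated blood loss (EBL) was determined using the difference in haematocrit values taken before and 48 hours after caesarean delivery". The fall is divided by the pre-operative value and multiplied by an estimated blood volume of 85 ml per kg.
- Haemoglobin: "As haematocrit values were not consistently available, EBL was also determined using the haemoglobin (Hb) value". The fall is divided by the end value and multiplied by blood volume.

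Transfusion appears as secondary outcome 3 in section 1.14.2: "Mean or median number of units of red blood cells transfused up to day 2 postpartum". It enters neither formula.

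Section 1.10 defends the calculated method on the ground that "any effects on the haematocrit of the physiological changes or IV fluids happened in all the participants". Of visual estimation it says "we used this together with the more objective calculated method for comparison to determine blood loss". Section 1.11 (Statistical Methods) contains no sensitivity analysis of the primary endpoint and no rule for transfused women.

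**The concern.** Both formulas infer blood loss from a fall in red-cell concentration between the day before surgery and day 2. Red cells transfused in between partly reverse that fall, and the formula reads the reversal as less bleeding.

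The defence in section 1.10 concerns influences shared by every participant. Transfusion is different: only some women receive it, often because they bled, so it is tied to the endpoint. It may also differ by arm. The trial is open-label, and section 2.3 (Justification) hopes that TXA will reduce the use of blood products.

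Some women who bled enough to be transfused can therefore drop out of the primary event count. If the same proportion of events is lost in each arm, the relative risk is unchanged; if not, it moves in either direction. Without a check by arm, a reader cannot tell whether the primary result depends on this.

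**Working it through.** **The plan's own figure.** The plan gives no figure for transfusion. Its sample size (section 1.4), from 2.1% and 5.8%, two-sided 5% and 90% power, reproduces: the printed formula gives 579.8 with z = 1.96 and 1.28, and 580.3 with unrounded z values, which rounds up to the stated 581 per group. Expected events are 581 × 0.021 ≈ 12 and 581 × 0.058 ≈ 34. For the 506 recruited in the initial period (section 1.6), taken as 253 per arm, they are about 5 and 15. Event counts are small, so a few masked women could matter.

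**Inputs from the plan.** The threshold is 1,000 ml. Blood volume is 85 ml/kg, used here for both formulas because the haemoglobin version does not define its own.

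**Assumptions, not in the documents.** Weight 70 kg; pre-operative haematocrit 36%; haemoglobin 12 g/dl; one unit contains 180 ml red cells or 60 g haemoglobin (range 120–240 ml, 40–80 g). Blood volume = 70 × 85 = 5,950 ml.

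**Haematocrit formula.** One unit raises haematocrit by 180/5,950 = 3.03 points.

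- Loss hidden = 5,950 × (180/5,950)/0.36 = 180/0.36 = 500 ml. Weight cancels. The range is 120/0.36 = 333 ml to 240/0.36 = 667 ml.
- Losses from 1,000 to just under 1,500 ml (upper limit 1,333 to 1,667) become no PPH.
- Example: 1,400 − 500 = 900 ml.

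**Haemoglobin formula, on its own scale.** One unit raises haemoglobin by 60/59.5 = 1.008 g/dl.

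- A score of 1,000 ml means end Hb = 12/(1 + 1,000/5,950) = 10.273.
- Without the unit, end Hb = 10.273 − 1.008 = 9.265, and the score is 5,950 × (12 − 9.265)/9.265 ≈ 1,756 ml (unrounded inputs).
- So one unit hides scores from 1,000 up to about 1,756 ml (1,487 at 40 g; 2,047 at 80 g). At 60 g the limit is 1,847 ml at 55 kg and 1,690 ml at 90 kg.
- Example: a score of 1,500 means end Hb 9.584; adding 1.008 gives 10.592, which scores 791 ml.

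**Same fall on both formulas.** A haematocrit score of 1,400 ml corresponds to end Hb 12 × (1 − 1,400/5,950) = 9.176, which the haemoglobin formula scores as 1,831 ml. After one unit the scores are 900 and 1,060 ml, so 500 and 770 ml are hidden. The haemoglobin formula does not mask less.

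**Not every transfused PPH is masked.** A score of 1,800 ml followed by one unit becomes 1,300 ml (haematocrit) or 1,035 ml (haemoglobin), still PPH.

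**Direction of bias, illustration only.** The planned relative risk is 0.021/0.058 = 0.36.

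| Events masked, TXA / control | Observed rates | Relative risk |
|---|---|---|
| 10% / 10% | 1.89% / 5.22% | 0.36 |
| 10% / 30% | 1.89% / 4.06% | 0.47 |
| 30% / 10% | 1.47% / 5.22% | 0.28 |

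These shares are invented to show direction. The planning rates come from a trial that used a haematocrit-calculated endpoint (section 2.2.4) and may already contain some masking, so no power loss is derived from them.

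**The case against.** The strongest case against is that harm is not shown. The documents give neither a transfusion rate nor a transfusion trigger. On the inputs above, the band hidden by one unit under the haematocrit formula corresponds to an untransfused day-2 haemoglobin of about 9.0 to 10.0 g/dl, and nothing shows that such women were transfused. This stands: the size of the effect is unknown.

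The illustration is also softer than one range suggests. Letting pre-operative haematocrit run from 30% to 40% widens the loss hidden by one unit to 300–800 ml (120/0.40 to 240/0.30). The cancellation of weight assumes that day-2 blood volume equals 85 ml/kg. If it were 1.25 litres lower, an illustrative use of the pregnancy plasma expansion quoted in section 1.10, one unit would hide 500 × 5,950/4,700 = 633 ml at 70 kg. This changes the size but leaves the mechanism intact.

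Safeguards exist. PPH by visual estimate is unaffected by transfusion. Units, additional uterotonics and emergency surgery are reported, and mean units times the number of women would cap how many could be masked. But section 1.10 itself calls visual estimation inaccurate, the estimate is unblinded, and none of these outcomes reclassifies a masked woman.

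Two further points are fair. No rule says which formula governs when both values exist; that is a separate gap, and the correction can be run on each formula. Also, the full protocol is held elsewhere and the data collection tool is not in the file, so the absence of a check is established only for this text.

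**Conclusion.** The concern holds. As written, the primary endpoint can record a transfused woman with true PPH as having none, and nothing in section 1.11 would reveal it. Under the stated assumptions one unit hides about 500 ml (333 to 667) on the haematocrit formula, and scores up to about 1,756 ml (1,487 to 2,047) on the haemoglobin formula. Those figures rest on assumed weight, haematocrit, haemoglobin and unit content. How many women are affected, which way the relative risk moves and what happens to power cannot be determined from the documents. This should be fixed, but it does not invalidate the design: the mechanism is certain, the impact is not, and a check is cheap.

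**What to change.** In sections 1.10 and 1.11, keep the primary calculation as it is and add a labelled sensitivity analysis of the primary endpoint and of calculated blood loss, corrected for recorded red-cell units to day 2:

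- Haematocrit formula: add (units × red-cell volume per unit) / pre-operative haematocrit as a fraction.
- Haemoglobin formula: replace the end value by end Hb − units × grams of Hb per unit / blood volume in dl.
- State the assumed content per unit and vary it over 120–240 ml or 40–80 g. In the examples above, the corrected loss is then 1,233–1,567 ml for the woman scored 900 ml, and 1,248–1,771 ml for the woman scored 791 ml.
- Report by arm the number of women transfused and the number reclassified.
- State that the haematocrit and haemoglobin change outcomes include any transfusion effect, and leave them as measured.

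Counting every transfused woman as PPH should be optional at most, because it brings an unblinded decision and transfusions for anaemia into the endpoint.

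The cost is a few sentences and one recalculation from data already listed. The downsides are the assumed content per unit and possible over-correction for units given after the day-2 sample. The analysis is also post hoc if added after the look described in section 1.11 ("An analysis was conducted after 506 participants had been recruited"), and should then be labelled so. Because the primary formula is kept, the statement in section 1.1 that "No changes were made to the trial design after commencement" is not disturbed, nor is comparability with the haematocrit-based source trial.

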1.11. STATISTICAL METHODS

Data analysis was conducted using Stata v15 (Stata Statistical Software: Release 15. College Station, TX: StataCorp LLC) following the CONSORT guidelines for reporting RCTs⁽⁵⁵⁾.

The primary analysis compared women given a low dose of TXA (10mg/kg) administered 10 minutes before elective caesarean section with prophylactic oxytocin administration to those given prophylactic oxytocin alone.

Baseline characteristics were compared between the groups to check the adequacy of randomization. Differences between patients lost to follow-up and included patients were also assessed. The intention-to-treat analysis was followed. This is a statistical concept whereby every participant in the study is accounted for in the analysis according to the randomization treatment assignment regardless of whether there is noncompliance, protocol deviations, withdrawal from the study, and anything happens after randomization⁽⁵⁶⁾.

Categorical data were reported using frequencies and proportions while continuous data were summarized using means and standard deviations for normally distributed data, and medians and quartile range where data was not normally distributed. Comparisons for categorical data were done using the chi-square test or Fisher's exact test when the sample size was small.

For continuous data, the t-test was used to compare differences between the groups and the analysis of variance (ANOVA) was used for comparing more than two groups. Where data were not normally distributed, the nonparametric Kruskal Wallis test was used to compare differences in continuous outcome for more than two groups. The Mann-Whitney U test was used to compare two groups where data were not normally distributed. Effect estimates were presented with relative risk measures and associated 95% confidence intervals. Any subgroup analysis was conducted as the primary analysis.

An analysis was conducted after 506 participants had been recruited to check if there are any significant differences in adverse events in the two groups.

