2.4. RESEARCH OBJECTIVES

1. To determine the effect of TXA (10mg/kg) given intravenously 10 minutes prior to an elective caesarean section on postpartum blood loss.
2. To determine the potential adverse effects of intravenous TXA given 10 minutes prior to elective caesarean section.

CHAPTER 3. RESEARCH METHODS

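### Post-operative laboratory values are compared without the pre-operative values already collected: unbiased, but possibly less precise than it need be

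*Combined protocol and SAP*

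**What the plan says.** Chapter 3, section 1.11 (Statistical Methods) sets out the comparisons. "For continuous data, the t-test was used to compare differences between the groups"; "The Mann-Whitney U test was used to compare two groups where data were not normally distributed". Categorical outcomes use chi-square or Fisher's exact test. ANOVA and Kruskal-Wallis are named only for more than two groups. No regression, covariate or hospital term appears. The one stated analytic use of baseline data is this: "Baseline characteristics were compared between the groups to check the adequacy of randomization".

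Section 1.10 (Assessment) records full blood count, U&E and liver tests on the day before delivery and on the second day after it. Vital signs are recorded before surgery, after placental delivery and 1 to 2 hours after birth.

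Section 1.14.2 (Secondary Outcomes) treats these measures in two ways. Among the TXA side effects it lists post-operative laboratory values alone, starting with "Post-caesarean delivery creatinine (mg/dL" and going on to urea, AST, ALT and bilirubin. Pre-surgery vital signs are listed there as items in their own right. Haemoglobin and haematocrit are defined as changes, for example "Difference between the haemoglobin on the day before surgery and at day 2 post-delivery".

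Section 1.6 (Randomization) allocates equal numbers to the two arms for the two hospitals. The first 400 numbers were split 200 per hospital; the split of the further 106 is not stated.

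**The concern.** Adverse effects are one of the trial's two objectives: "To determine the potential adverse effects of intravenous TXA given 10 minutes prior to elective caesarean section". Section 1.11 adds: "An analysis was conducted after 506 participants had been recruited to check if there are any significant differences in adverse events". A safety comparison that finds no difference is only as informative as its interval is narrow. For the laboratory values, each woman's own pre-operative result is normally the best available predictor of the post-operative one, and it has already been collected. Leaving it out puts predictable between-woman variation into the error term. Baseline is used for haemoglobin and haematocrit (as a change) and not for the chemistry, and no reason is given. Hospital, which organised the allocation, is also left out.

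**Working it through.** **1. The plan's own figure.** Section 1.4 gives 581 per group for PPH of 2.1% against 5.8%, two-sided 0.05, 90% power, 1:1. The Fleiss formula with exact normal quantiles gives 581 (580 with the printed 1.96 and 1.28), so the figure is reproduced.

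**2. Inputs for the precision check.** 506 women recruited (section 1.6), taken as 253 per group. The pre/post correlation rho is not in the documents, so 0.1 to 0.7 is assumed. Creatinine is taken to be part of the U&E panel, whose contents are not itemised.

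**3. Laboratory values: t-test on the post-operative value against ANCOVA.** The variance ratio is 1 − rho². The standard error in SD units is √(2/253) = 0.0889. Unadjusted, the 95% half-width is 1.96 × 0.0889 = 0.174 SD, and the difference detectable with 80% power is (1.96 + 0.842) × 0.0889 = 0.249 SD. Both are multiplied by √(1 − rho²):

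| rho | variance reduction | half-width (SD) | detectable (SD) | equivalent n per group, 253/(1 − rho²) |
|---|---|---|---|---|
| 0.1 | 1% | 0.173 | 0.248 | 256 |
| 0.2 | 4% | 0.171 | 0.244 | 264 |
| 0.3 | 9% | 0.166 | 0.238 | 278 |
| 0.5 | 25% | 0.151 | 0.216 | 337 |
| 0.7 | 49% | 0.124 | 0.178 | 496 |

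Simulation with 253 per group gave variance ratios of 0.93, 0.75 and 0.52 at rho 0.3, 0.5 and 0.7, against 0.91, 0.75 and 0.51 from the formula.

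**4. Skewed values.** If values are lognormal (assumed) and Mann-Whitney is used, its efficiency relative to a log-scale t-test is 3/π = 0.955. Log-scale ANCOVA then lowers variance by 1 − 0.955 × (1 − rho²) = 13%, 28% or 51% at rho 0.3, 0.5 or 0.7.

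**5. Missing baselines.** With simple imputation and a fraction m missing at random, the reduction is about (1 − m) × rho². At rho 0.5 and m = 0.3 (assumed) it is 0.7 × 0.25 = 17.5%, not 25%.

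**6. Haemoglobin and haematocrit.** These are already changes. With k the ratio of post- to pre-operative SD, ANCOVA lowers the change-score variance by 1 − k²(1 − rho²)/(1 + k² − 2·rho·k). At k = 1 this is 35%, 25% or 15% for rho 0.3, 0.5 or 0.7. At k = 1.25 it is 22%, 11% or 2%, and 0% at rho 0.8. The 24-hour effects in the open Egyptian trial (section 2.2.4) are 1.42 − 0.48 = 0.94 g/dl and 4.30 − 1.82 = 2.48 points. The pooled SDs are √((0.87² + 1.16²)/2) = 1.025 and √((2.93² + 3.64²)/2) = 3.304. Unadjusted, those effects are 0.94/(1.025 × 0.0889) = 10.3 and 2.48/(3.304 × 0.0889) = 8.4 standard errors. At such effects the gain decides nothing.

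**7. PPH.** At 253 per group the plan's formula gives z = (0.037 × √253 − 1.96 × 0.2755)/0.2742 = 0.177, power 57.0%. Suppose, as an extreme, that the hospitals' rates were 1.0% and 6.9%. Hospital then explains 0.0295²/(0.0395 × 0.9605) = 2.3% of the variance. The effective n is 253/0.977 = 259, and power is 58.0%. With rates of 3.0% and 4.9% it is 57.1%. Prognostic covariates beyond hospital would also add little: if they explain 5%, 10% or 25% of latent blood-loss variance (assumed), power by a Wald approximation goes from 57.4% to 57.8%, 58.3% or 60.2%.

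**The case against.** The strongest reply is that this is a preference and not an error. Unadjusted tests are valid under randomisation and contradict nothing else in the document. That stands, and it sets the weight of the point.

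Three further objections narrow it:

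- **Counted harms.** Most named harms in section 1.14.2 are numbers of participants: headache, hypotension, thrombosis, seizures, and renal failure defined by dialysis. ANCOVA does nothing for these, so the link to the analysis at 506 women is only partial.
- **Size.** The correlation is unknown. At 0.1 to 0.2, plausible for vital signs just after delivery under anaesthesia, the gain is 1% to 4%. Section 1.10 says haematocrit was not consistently available, and incomplete baselines would reduce the gain further.
- **Consequence.** The documents give no laboratory margin against which a half-width of 0.174 SD is too wide, so no decision is shown to change.

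A related remark should be kept apart. "Effect estimates were presented with relative risk measures and associated 95% confidence intervals", so no difference with an interval is specified for continuous outcomes. That is a reporting gap which needs no covariate to repair, and it adds no weight here.

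Finally, section 3.20 says the full protocol is held elsewhere, so the absence of adjustment is shown for this document only.

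What survives is that the baselines were collected, adjustment costs almost nothing, and in a sample of this size ANCOVA is in effect no less precise than either comparison it would replace.

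**Conclusion.** The point holds as an optional, low-priority improvement. The plan may lose precision on post-operative creatinine, urea, AST, ALT and bilirubin, by anything from a negligible amount to about half the variance. The size depends on a correlation that the documents do not give, on an equal split of the 506 women, and on complete pre-operative results.

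A reader might infer more, and the documents do not support it:

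- That the stated comparisons are biased: randomisation protects them.
- That adjustment would repair the shortfall in PPH power at 506 women: hospital adjustment is worth about one point.
- That the conclusions on thrombosis, seizures or other counted side effects are weakened: they are untouched.
- That baseline is ignored throughout: haemoglobin and haematocrit are compared as changes, and calculated blood loss already contains the pre-operative value and body weight.
- That vital signs certainly lose precision: the document does not say whether the pre-surgery readings preceded TXA, and the correlation may be low.

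**What to change.** - **Model.** Analyse each post-operative laboratory value by ANCOVA with treatment, hospital and the same measure's pre-operative value, on the log scale if skewed. Report the adjusted mean difference, or ratio of geometric means, with a 95% CI.
- **Missing baselines.** Use simple imputation, so that no randomised woman is dropped for want of a covariate.
- **Other measures.** Apply the same model to day-2 haemoglobin and haematocrit. Apply it to post-delivery vital signs only if the pre-surgery readings were taken before TXA.
- **The 506 women already analysed.** Keep the stated tests as the main analysis. Add the adjusted results as supportive and labelled post hoc, after checking how the further 106 numbers were split between the hospitals.
- **If recruitment continues.** Prespecify the adjusted model for the final analysis of all women. Choose the covariates from the measurements listed in section 1.10, not from the results seen so far.

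The cost is low: a paragraph of SAP text, a missing-baseline rule, checks of the allocation lists and vital-sign timing, and modest extra analysis. No new data are needed, and nothing need change for PPH or the counted side effects on this ground.
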